Diagnosis & Key Eligibility Criteria	Patients must have a histologically documented (either primary or metastatic site) diagnosis of breast cancer that is HER2 negative (expansion cohort only TNBC allowed). Patients must have stage IV disease and must have completed at least one line of chemotherapy. Only TNBC patients will be enrolled in the expansion cohort. Also, only PD-L1 negative patients in the front line setting will be enrolled. Beyond frontline setting, any PD-L1 status is acceptable. . Patients must be ECOG performance status of 2 or less and have normal organ function. Patients treated with previous immunotherapies are excluded.
Treatment Plan	Patients will be treated with durvalumab 1500mg intravenously (IV) every 4 weeks for a total of 4 doses, and tremelimumab 75mg IV every 4 weeks for a total of 4 doses. After completion of the 4 doses of combination therapy, durvalumab will be continued at a dose of 750mg every 2 weeks for up to 18 additional doses, or until progressive disease or unacceptable toxicity. The first 750mg dose of durvalumab will be 4 weeks after the last combination dose. Patients will be followed for 3 years for survival and progression of disease.

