### 1.2 **Breast Cancer Immunology**

The breast tumor microenvironment is often infiltrated by immune cells. The adaptive immune system can identify tumor antigens through immunosurveillance [7]. In this process, antigen-presenting cells present non-self antigens to T cells, which allow them to recognize and destroy cells expressing such antigens. A hallmark of oncogenesis is that tumor cells can develop mechanisms to evade such immune recognition [8, 9].

The presence of tumor infiltrating lymphocytes (TILs) has been associated with more favorable prognosis in breast cancer [10]. Paradoxically, TILs have been closely associated with ER negative subtypes, tumors with an aggressive biological behavior. However, this discrepancy may be due to the fact TILs are associated with better survival in basal-like rather than non-basal-like TNBC [11, 12]. Nevertheless, these results highlight the importance of immune regulatory mechanisms in the pathogenesis of breast cancer.

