Expression of PD-L1 is known to be associated with poor prognosis in patients with breast cancer, particularly those with luminal B and basal-like subtypes [24], thus making aggressive phenotype ER positive and triple negative breast cancers attractive subtypes in which to investigate PD-L1 blockade. A subsequent phase 1B study presented at the 2014 San Antonio Breast Cancer Symposium demonstrated that in patients with heavily pretreated metastatic triple negative breast cancer (TNBC) treated with the humanized IgG4k isotype mAb against PD-1, pembrolizumab, 16.1% had a partial response (PR), and 9.7% had stable disease (SD) [25].

Through the years, the clinical landscape has evolved. Original study ([name] et al Oncotarget 2018) found that patients who responded had only had 1 line of prior therapy. We thus want to limit to no more than 1 line of previous therapy in the metastatic setting. Indeed several studies have now shown that responses to immune checkpoint inhibition are mostly restricted to earlier lines settings ([name] et al JNCCN 2019).

Currently, atezolizumab in combination with nab-paclitaxel is FDA-approved for patients with no prior treatment for metastatic TNBC who are PD-L1 immune cell-positive. The ImPassion130 study (Schmid et al NEJM 2018) suggests that these patients benefit from the addition of atezolizumab to nab-paclitaxel in the front line setting. Therefore, now we wish to exclude patients who are PD-L1-positive in the front line setting. Patients who are PD-L1-negative are eligible for this protocol in the front line setting, if patients are enrolled in the second line setting, PDL1 status is not needed for enrollment.

Although effects of single agent checkpoint blockade are modest, with only a small fraction of patients having significant responses, recently combination checkpoint blockade with CTLA-4 and PD-1 inhibitors has demonstrated synergistic activity with an overall response rate of 40%, and 31% of patients achieving >80% reduction in their tumors by 12 weeks [26]. A recently presented phase 1 open-label study evaluating the anti-PDL1 inhibitor, durvalumab, in combination with tremelimumab in patients with advanced non-small cell lung cancer, revealed that the combination was well tolerated with 75% of reported adverse events (AEs) being low grade, and only 3/24 patients discontinuing therapy due to treatment-related AEs. Furthermore, patients experienced an

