**1.7.3 Rationale for Expansion Cohort**

Based on initial portion of the study where the first 18 evaluable patients were investigated, a striking difference between overall response rates in ER-positive and TNBC was observed (Table 1). The ORR in ER-positive was 0%, and in TNBC it was 42.9%. Furthermore, the TNBC group had 2 patients with SD (clinical benefit rate of 71.4%), and one of the patients listed as PD, in fact had pseudoprogression (after 2 months had sub-centimeter LNs enlarge to >15mm, captured as PD per RECIST, but afterwards experience stability in these lesions, and a PR in target lesions). While the numbers are small, there is a clear signal in the TNBC cohort since essentially 6 out of 7 patient experienced clinically relevant benefit. Immunotherapy is rapidly evolving in breast cancer, and these initial results show promise in this cohort of patients, and the rationale of the expansion cohort is to capitalize on this initial experience.

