### **2.3 Exploratory Objectives & Endpoints**

2.3.1 To evaluate if serum and tissue-based biomarkers including: circulating tumor DNA, immunohistochemical expression of PD-L1; tumor infiltrating lymphocytes (TILs); changes in tissue and peripheral T cell receptor genotype; mutational and neoantigen burden; and immune-related candidate gene expression signatures predict response to durvalumab in combination with tremelimumab.

2.3.2. To determine the response rate (RR) and duration of response(DoR) of subsequent next line therapy after progression on durvalumab/ tremelimumab study regimen, for those patients who are able to submit detailed follow up data about subsequent treatment and response.

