**3.1 Inclusion Criteria**

3.1.1 For the expansion cohort: Only metastatic TNBC patients will be enrolled.  
*[Please note: the General cohort had enrolled patients with the following criteria: Patients must have a histologically documented (either primary or metastatic site) diagnosis of breast cancer that is HER2 non-overexpressing by immunohistochemistry, namely 0 or 1. If they have an equivocal immunohistochemistry, 2, the tumor must be non-gene amplified by FISH performed upon the primary tumor or metastatic lesion (ratio <2 and HER2 copy number <4). ER positivity is defined as 1% or greater (29). PR positivity will be defined as a result of greater than 10%. Documentation of ER and PR status should be available at registration.]*

3.1.2 Patients must have measurable disease by RECIST 1.1 criteria.

3.1.3 Patients must be one of the following :

- Have been treated with at least one prior chemotherapy regimen in the metastatic setting
- Within 12 months of their last adjuvant systemic treatment and are felt to be chemotherapy refractory.
- PD-L1-negative in the front line setting.  
*[Note: Beyond frontline, any PD-L1 status is acceptable]*

*Note: please submit the PD-L1 test with the pathology report at registration.*

3.1.4 Completion of prior chemotherapy systemic anticancer therapy at least 2 weeks prior to study entry.

3.1.5 Radiation therapy must be completed at least 2 weeks prior to study entry. Radiated lesions may not serve as measurable disease unless they have been radiated  $\geq$ 12 months prior to enrollment.

3.1.6 Patients may have parenchymal brain metastases if stable (no evidence of progression) for at least 1 month after local therapy (radiation or surgery). Leptomeningeal disease is excluded. Must have completed any prescribed

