#### **10.3**

#### **Data Analyses Plans**

The primary analysis will be on the intent-to-treat (ITT) population, including all evaluable patients. Best ORR defined as will be defined as number (%) of patients with at least one visit response of complete or partial response by the Response Evaluation Criteria in Solid Tumors (RECIST 1.1). Best objective response prior to disease progression will be used. The overall response rate will be estimated by the proportion of overall response, and its 80% confidence interval (CI) and 95% CI will be estimated using the exact binomial distribution.

Additionally, we will evaluate clinical benefit rate, defined as stable disease for  $\geq 12$  weeks complete or partial response using RECIST 1.1 guidelines in a similar manner. We will also perform similar analyses using Immune Related RECIST (irRECIST).

PFS is defined as the time from date of treatment initiation until date of documented disease progression or death (by any cause in the absence of progression). OS is defined as the time from the date of start of treatment until death due to any cause. For patients alive at the time of data cut-off, PFS and OS will be censored as of the last tumor assessment date or known to be alive, respectively. The PFS and OS will be estimated using the Kaplan-Meier method. The number, frequency, and severity of adverse events (as defined by the NCI Common Terminology Criteria for Adverse Events or CTCAE version 4.03) will be recorded.

Baseline percent PDL1 expression, TILs (sTILs, iTILs, and their ratio), and changes in T cell subpopulations will be used as a continuous variable to predict clinical benefit or overall response rates using appropriate statistical summaries. Cox proportional hazards regression will be used to compare how these biomarkers are associated with PFS and OS as well.

Changes from baseline in these biomarkers will also be analyzed to assess for pharmacodynamic effects of treatment. Continuous variables will be analyzed using either paired t-tests, signed rank tests or repeated measures analysis of variance.

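### Section 10.3 relates PD-L1, TILs and T-cell changes to outcome without restricting to or stratifying by receptor status, so a marker of TNBC can pass for a predictor of response

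*Combined protocol and SAP*

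**What the plan says.** Section 2.3 asks whether a list of serum and tissue markers, including PD-L1, TILs and "immune-related candidate gene expression signatures predict response to durvalumab in combination with tremelimumab". The analysis is in section 10.3. Baseline percent PD-L1, TILs and changes in T-cell subpopulations "will be used as a continuous variable to predict clinical benefit or overall response rates using appropriate statistical summaries", and "Cox proportional hazards regression will be used to compare how these biomarkers are associated with PFS and OS as well". Neither section limits the analysis to a cohort or subtype, or names a stratification factor or covariate. The only split by receptor status is in section 10.2, where ORR is also to be calculated separately by receptor status. The same section says that the design is not stratified by estrogen receptor status.

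The protocol gives the background facts itself. Section 1.7.3 reports for the first 18 evaluable patients that "The ORR in ER-positive was 0%, and in TNBC it was 42.9" per cent; the accompanying table gives 0 of 11 and 3 of 7. Section 1.2 states that "TILs have been closely associated with ER negative subtypes".

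On PD-L1 and line of therapy, the Study Summary says that "only PD-L1 negative patients in the front line setting will be enrolled", and section 3.1.3 adds that "Beyond frontline, any PD-L1 status is acceptable". Section 1.3 says that "responses to immune checkpoint inhibition are mostly restricted to earlier lines settings".

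**The concern.** Receptor status is related to response (0/11 against 3/7) and, on the protocol's own account, to TILs. That makes it a confounder of the TIL-response association in any sample containing both subtypes. The general cohort is such a sample, with 14 ER+ and 14 ER- evaluable patients planned. An analysis that ignores receptor status would credit the marker with what belongs to the subtype. The objective is to find out which patients respond, so the likely error is to report as a predictive marker something that only identifies TNBC, which is already known from pathology.

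A second, weaker link concerns PD-L1 in the expansion cohort. If PD-L1-positive patients enter almost only after prior treatment, and response depends on line, then the PD-L1 estimate carries a line effect.

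**Working it through.** **Plan's figures.** 3/7 = 42.9%, 0/11 = 0% and 3/18 = 16.7%, as in the section 1.7.3 table. The marker analysis has no stated sample size or effect size to reproduce.

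**Receptor status: inputs.** ORR is 3/7 in TNBC and 0 in ER+ (section 1.7.3). Sample sizes are 14 TNBC and 14 ER+ (general cohort, counting the ER- patients as TNBC), or 34 and 14 after adding the 20 expansion patients. Assumed, because the documents give no figure: TIL-high in 60% of TNBC and 20% of ER+, with no TIL effect within either subtype (true odds ratio 1).

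**Formula.** Responders among TIL-high = n(TNBC) × prevalence in TNBC × 3/7; TIL-low likewise with 1 − prevalence. Odds ratio = odds of response in TIL-high ÷ odds in TIL-low.

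- 14/14, TIL-high: 14 × 0.6 × 3/7 = 3.6 responders of 8.4 + 2.8 = 11.2 (32.1%). TIL-low: 2.4 of 5.6 + 11.2 = 16.8 (14.3%). Odds ratio = (3.6/7.6)/(2.4/14.4) = 2.84.
- 34/14, TIL-high: 8.74 of 23.2 (37.7%). TIL-low: 5.83 of 24.8 (23.5%). Odds ratio = (8.74/14.46)/(5.83/18.97) = 1.97.

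| TIL-high, TNBC / ER+ (assumed) | 14/14 | 34/14 |
|---|---|---|
| 60% / 20% | 2.8 | 2.0 |
| 50% / 30% | 1.7 | 1.4 |
| equal | 1.0 | 1.0 |

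**Continuous scale.** Section 10.3 uses the marker as a continuous variable, so a pooled two-sided 5% Wilcoxon test was also simulated (4,000 trials per setting, no effect within subtype, TNBC ORR 42.9%). TILs were set higher in TNBC by 0.5 to 1 SD (assumed). With ER+ ORR 0%, the pooled test rejects in 8% to 21% of trials at 14/14 and 9% to 20% at 34/14. With ER+ ORR 10%, the range is 7% to 14%. Within TNBC it rejects in 3.5% to 5.0%.

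**PD-L1 and line.** The documents give no front-line ORR and no front-line share. Assume 20 expansion patients, 10 of them front line and all PD-L1-negative. Among the 10 later-line patients, take 4 PD-L1-positive with ORR 30% and 6 negative with ORR 15%. The within-line odds ratio is (0.30/0.70)/(0.15/0.85) = 2.4. With front-line ORR f, the pooled PD-L1-negative ORR is (10f + 6 × 0.15)/16.

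| Assumed f | PD-L1-negative ORR | Pooled odds ratio |
|---|---|---|
| 15% | 15.0% | 2.4 |
| 25% | 21.3% | 1.6 |
| 30% | 24.4% | 1.3 |
| 40% | 30.6% | 0.97 |

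The bias runs from nothing to complete masking, depending on f. Other inputs move it further. With later-line PD-L1-negative ORR 10%, PD-L1 prevalence 20%, half the patients front line and f = 30%, a true odds ratio of 2 appears as 0.83.

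**Numbers available.** Section 1.3 puts PD-L1 expression at about 20% of TNBC. Of 20 expansion patients with 25%, 50% or 75% front line, the expected PD-L1-positive count is 15 × 0.2 = 3, 10 × 0.2 = 2 or 5 × 0.2 = 1.

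**The case against.** **Section 10.3 never says that subtypes or cohorts are pooled, and its wording does not forbid stratifying.** True. But no other analysis set is named, and the general cohort alone mixes subtypes. The expansion cohort is TNBC only, so receptor confounding is absent there, and adding it dilutes the problem (2.8 falls to 2.0).

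**The work is exploratory and small.** Also true. There is no power claim or decision rule attached to it. Sampling error will exceed the bias for PD-L1, and stratified results can only be descriptive. That supports labelling them so; it does not support an estimate confounded by a factor known in advance.

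**A reader might infer that eligibility ties PD-L1-negative status to the better-responding line and so reverses the PD-L1 result.** The documents do not support this. Section 1.3 reports that responders in the original study had one prior line, which is later than front line, and no front-line ORR is given anywhere. With the inputs tabulated above, reversal needs a front-line ORR of about 39% or more. The tie is also incomplete: the section 3.1.3 criterion for patients within 12 months of adjuvant treatment carries no PD-L1 condition. The rule came in with Amendment 11 (10.29.19), and Appendix E records closure on 7.20.2020 for low accrual, so few patients may be affected.

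**A reader might also infer that the two biases offset each other.** As described they concern different markers, TILs through subtype and PD-L1 through line, so no such claim can be made.

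**Conclusion.** The concern holds for receptor status. As written, section 10.3 allows a marker with no effect within subtype to appear predictive. The expected spurious odds ratio is about 2.8 at 14/14 and 2.0 at 34/14 if TIL-high prevalence is 60% and 20%. It is 1.7 and 1.4 at 50% and 30%, and there is none if prevalences are equal. These figures rest on the assumed prevalences and on interim ORRs from 7 and 11 patients holding; a non-zero ER+ ORR would reduce them.

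The line-of-therapy point is secondary. Bias in the PD-L1 estimate is possible for patients enrolled under the current rule if response differs by line, but its direction and size cannot be fixed from the documents. The primary ORR conclusion is untouched. Even after stratification, a single arm cannot separate a predictive from a prognostic marker.

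**What to change.** In section 10.3:

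1. State the analysis set. Run the marker-response and clinical-benefit analyses within TNBC, or stratified by receptor status, and stratify the Cox models by receptor status.
2. For PD-L1, report the association among previously treated patients, where both PD-L1 classes are eligible, and show front-line PD-L1-negative patients separately.
3. Label all these results descriptive.

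The cost is a few sentences of SAP text. Section 3.1 already asks for ER and PR documentation (general cohort) and the PD-L1 test at registration. Prior treatment must be known to apply section 3.1.3, although line is not listed as a registration item and should be confirmed as a recorded variable. The statistical price is wider intervals, with perhaps one to three PD-L1-positive expansion patients in the previously treated group.

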**4.0 TREATMENT PLAN**

**4.1 Overview**

Non-randomized, open-label, pilot phase II clinical trial of durvalumab in combination with tremelimumab in patients with stage IV HER2 negative breast cancer, with an expansion cohort of TNBC.

Patients will be treated durvalumab 1500mg intravenously (IV) every 4 weeks for a total of 4 doses, and tremelimumab 75mg IV every 4 weeks for a total of 4 doses. After completion of the 4 doses of combination therapy (induction phase), durvalumab will be continued at a dose of 750mg every 2 weeks for up to 18 additional doses (maintenance phase), or until progressive disease (see 4.1.1) or unacceptable toxicity. The first 750mg dose of durvalumab will be 4 weeks after the last combination dose. Patients may continue on therapy after progression or after initial 52 week treatment period as specified in Sections 4.1.1 and 4.1.2. Patients will be followed for 3 years or until time of death. Overall response rate (ORR), clinical benefit rate, PFS, and OS will be determined. In addition, patient's next line of therapy will be monitored for response rates and duration of clinical benefit to next line therapy.

Patients will undergo a fresh tissue biopsy prior to study enrollment and two months after treatment, unless deemed to be clinically inappropriate per PI or co-investigator, to evaluate pharmacodynamic changes in immune-related biomarkers. Correlatives will be assessed.

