For analysis of each T cell receptor clonotype, we will apply a newly-developed algorithm Bowtie2 aligner (Ref; Nature methods 2012; 9:357-9), in collaboration with Profs. [name] and [name] in Human Genome Center, The University of Tokyo. We will assign each of V, (D), J and C segments in the TCRA and TCRB reference sequences provided by IMGT/GENE-DB (Ref; Nucleic acids research 2005; 33:D256-61). By our approach, we will also identify novel exons that are not deposited in the reference sequence database. After decomposition of T cell receptor sequencing reads into V, (D), J and C segments, we will determine amino acid sequences of CDR3 (complementarity determining region 3), which plays a critical role in recognition of antigen. We will also calculate the diversity index (inverse Simpson's index) in CDR3 sequences to assess overall diversity and clonality in the T cell receptor clonotypes. Descriptive statistics will be used to assess differences from baseline to two months, and their relationship with clinical endpoints.

Determination of response rate to subsequent next line therapy will be determined in a similar manner as to the primary objective when feasible, where ORR is defined as number (%) of patients with at least one visit response of PR or CR. In instances where data for this post-hoc analysis cannot be obtained and only clinical responses can be obtained (ie patient followed up at an outside institution and only clinical radiograph reports are available), these will be used. Best objective response prior to disease progression will be used. Response rates will be calculated using proportions and the 80% and 95% confidence intervals will be estimated using the exact binomial distribution. Duration of response to next line therapy will be defined as date from next line therapy until date of last dose of next line therapy. The Kaplan-Meier method will be used to assess duration of response to next line therapy.

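### Section 10.3 defines duration of response to next-line therapy as start of therapy to last dose, which is time on treatment and not the duration of response named in objective 2.3.2

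*Combined protocol and SAP*

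**What the plan says.** Objective 2.3.2 is "To determine the response rate (RR) and duration of response(DoR) of subsequent next line therapy after progression" on the study regimen, "for those patients who are able to submit detailed follow up data about subsequent treatment and response". Sections 1.8, 6.4 and 10.1 repeat this objective.

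The only operational definition is in Section 10.3, where this duration "will be defined as date from next line therapy until date of last dose of next line therapy". An estimator follows: "The Kaplan-Meier method will be used to assess duration of response to next line therapy". For the response rate, the same paragraph uses the primary-endpoint definition, "where ORR is defined as number (%) of patients with at least one visit response of PR or CR", and adds: "Best objective response prior to disease progression will be used".

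Section 4.1 uses another label: the patient's "next line of therapy will be monitored for response rates and duration of clinical benefit to next line therapy".

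The one censoring rule in Section 10.3 is written for PFS and OS. None is given for the next-line duration, and no sentence says which patients enter its curve.

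**The concern.** Duration of response describes how long a response lasts once it has been achieved. It needs a documented response to start the clock and loss of that response to stop it. The rule in Section 10.3 uses neither. Followed as written, it gives a Kaplan-Meier curve of time on treatment under the name of duration of response, and a reader would take it for the latter. The objective was added because notable responses had been seen on chemotherapy after progression, so how long those responses last is the question of interest. The direction of the error depends on how next-line treatment is given and stopped, which the documents do not describe, so a reader could not correct for it.

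**Working it through.** No sample size, power or error rate in the documents depends on this definition, so there is no stated figure to reproduce. The check compares the text, then illustrates on assumed inputs.

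**1. The definition beside its objective**

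| Element | Duration of response (objective 2.3.2) | Rule in Section 10.3 |
|---|---|---|
| Clock starts | First documented PR or CR | Start of next-line therapy |
| Clock stops | Progression or death | Last dose |
| Population | Patients with PR or CR | Not stated |
| Censoring | Needed | Not stated |

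The protocol itself separates the last dose from loss of response. Under Section 4.1.2, a patient still in response or stable at 52 weeks may stop study treatment and be followed. Section 4.6 lists adverse events and patient choice as reasons to stop, apart from progression. In Section 10.3, PFS ends at progression or death.

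**2. Size of the difference in one responder**

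Let S be the start of the next line, R first response, L last dose and P progression.

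Rule − duration of response = (L − S) − (P − R) = (R − S) − (P − L)

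The rule is too long by the time to response and too short by the time from last dose to progression. Assumed examples, in weeks from S:

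- Treated close to progression (R = 8, L = 21, P = 24): rule 21, duration of response 24 − 8 = 16. Difference 8 − 3 = +5.
- Stopped early (R = 8, L = 18, P = 48): rule 18, duration of response 48 − 8 = 40. Difference 8 − 30 = −22.
- Non-responder (L = 6, P = 8): rule 6, duration of response undefined.

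**3. Medians in responders**

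Assumptions, none of them from the documents: response seen at month 2; duration of response D exponential with median 6 months; treatment runs to progression or to a course limit of c months.

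- Treated to progression: the rule gives 2 + D, with median 2 + 6 = 8 months.
- Course limit c: the rule gives min(2 + D, c). The share reaching the limit is 2^(−(c − 2)/6), which is 2^(−2/6) = 0.79 for c = 4 and 2^(−4/6) = 0.63 for c = 6. Both exceed one half, so the median is the limit itself, 4 or 6 months.

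The rule matches the true 6 months only when the limit happens to be 6. A separate simulation in weeks (response at week 8, true median 24) behaves the same way: 32 weeks if treated to progression, 18 if treatment stops by week 18.

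**4. If non-responders also enter**

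This is conditional on a population that the plan does not state. Further assumptions: non-responders' time on treatment is exponential with median 2 months, and responders are treated to progression. With response rate p, the median t solves, for t above 2,

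(1 − p)·2^(−t/2) + p·2^(−(t − 2)/6) = 0.5

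This gives t of about 2.7, 3.1 and 4.3 months for p = 20%, 30% and 50%. Check at p = 20%, t = 2.7: 0.8 × 0.392 + 0.2 × 0.922 = 0.498.

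**The case against.** The strongest reply is that this may be a deliberate, practical proxy. Section 4.1 speaks of duration of clinical benefit, and Section 10.3 expects that some patients will be followed elsewhere with only clinical radiograph reports available. On that view the fault is mainly the label. Much of this stands, and it is why renaming comes first in the fix. It does not rescue the definition, because objective 2.3.2 and Section 10.3 both call the quantity duration of response.

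A second reply is that the endpoint carries little weight. It is exploratory, its own paragraph calls it post hoc, it covers only patients with usable data, and no hypothesis or decision rests on it. Appendix E (Amendment 12) records closure for low accrual in July 2020. This stands as a limit on importance. The result could still be reported, and an exploratory result needs a correct name.

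A third reply is that all the medians above come from assumed inputs, and that the capped results simply return the assumed cap. This is right. They show direction and possible size, and they do not estimate this trial.

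A reader might also infer that the plan puts every patient on the curve, so that each non-responder is given a duration of response. The documents do not say so. Section 10.3 has no population sentence for this endpoint, its wording can be read as covering responders only, and objective 2.3.2 limits the set to patients with follow-up data. The text fails to exclude non-responders, which is a gap and not a stated rule.

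**Conclusion.** The definition is wrong for the objective as written, and no other section corrects it. What would be estimated is time on next-line treatment. Among responders it differs from duration of response by the time to response less the interval from last dose to progression, so it can err in either direction: about 8 or 4 months against a true 6 on the stated assumptions. The conclusion rests on the text and does not need those figures. The lower medians in step 4 apply only if non-responders are entered.

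The missing censoring rule adds to the problem: a patient still on next-line therapy at data cut-off has no defined handling, and the latest recorded dose could be counted as an event.

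A reader might infer that the trial's efficacy conclusions are affected. They are not: ORR, clinical benefit rate, PFS and OS on the study regimen have their own definitions and do not use this one. The point is worth correcting before any next-line result is reported, and its consequence is confined to that exploratory result.

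**What to change.** In Section 10.3:

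- Rename the present measure *time on next-line treatment* and state who enters it. Censor patients still on therapy at last contact. This needs only dosing dates.
- Where dated next-line assessments are available, report duration of response in patients with PR or CR, from first documented response to progression or death, censored at the last disease assessment.
- If those dates cannot be obtained, say that duration of response to next-line therapy cannot be estimated.
- Use the same term in Sections 4.1, 2.3.2, 6.4 and 10.1.

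The cost is more than a change of wording. Fewer patients enter the duration-of-response curve, and dated response and progression on the next line are required. Section 10.3 already presumes some of this, since best response is taken before progression. However, the Section 5.0 table marks collection of next-line therapy and response only through the 3-month visit and marks no scans after the off-treatment visit. Section 4.8 ends study observation once another anticancer treatment begins, which is when the next-line clock starts. Section 4.7 plans longer follow-up for survival and progression, and footnote 8 of the Section 5.0 table allows it by phone. These provisions must be reconciled with the objective.
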